## Summary of research scheme

Program name	Based on long-term survival outcomes of primary non-ampulla duodenal adenocarcinoma
Applicant	Nanfang Hospital of Southern Medical University
Principal investigator	[name]
Study center and director	Southern Medical University Nanfang Hospital [name]
Object of study	Duodenal adenocarcinoma (DA) patients
Objective	
Main Objective: To determine whether radical DA resection is associated with an improvement in 5-year overall survival
 
Secondary objectives: Adjuvant therapy, pancreatic invasion, and advanced tumor stage were identified as significant predictors of overall survival

Study group	Histologically confirmed non-ampulla DA (including all stages of disease at diagnosis)
Study design	Retrospective cohort study
Study duration	2024.04-2024.06
Sample size	400 cases
Inclusion criteria	
(1)At least 18 years old;
 
(2)Voluntary signing of informed consent;
 
(3)Non-ampulla DA patients were diagnosed according to the Chinese Medical Association's Clinical Diagnosis and Treatment Guidelines for Gastrointestinal Tumors (2022 edition), including patients at all stages of diagnosis;
 
(4)Unless there is no other malignant tumor diagnosed in the ampulla DA.

Exclusion criteria	
(1)Cancer of the ampulla or other forms of gastrointestinal cancer
 
(2)Incomplete medical records
 
(3)Missing diagnostic or therapeutic data
 
(4)Follow-up was lost shortly after diagnosis

Efficiency analysis	
Primary outcome measures for effectiveness analysis: median overall survival, 3 - and 5-year overall survival rates in the cohort
 
Secondary outcome measures for effectiveness analysis: Overall survival with adjuvant therapy, pancreatic invasion, and advanced tumor

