Statistic analysis	
Statistical analysis
 
Rigorous statistical methods were used to analyze the collected data. Survival outcomes, including OS and DFS, were calculated from the date of diagnosis until the date of death or last follow-up, and from the date of diagnosis until the date of disease recurrence or last follow-up of DFS. Kaplan-Meier survival curves were generated to illustrate survival trends over time, and log-rank tests were used to compare the distribution of survival among different patient subgroups. Cox proportional hazard models were used to identify independent prognostic factors affecting survival. Variables considered in the model included demographic factors (age, sex), clinical features (BMI, jaundice, bleeding, anemia), preoperative laboratory values, treatment details (radical resection, adjuvant therapy), and pathological findings (AJCC stage, tumor differentiation and lymph node involvement rate). Hazard ratios (HRs) and 95% confidence intervals (CI) were calculated to estimate the strength of the association between each variable and survival outcomes.

Follow-up visit	The patients included in this study were from a hospital cohort that included cases diagnosed and treated in the Department of General Surgery at Nanfang Hospital of Southern Medical University. Inclusion criteria were histologically confirmed non-ampulla DA, including all stages of disease at diagnosis. Patients were excluded if they had ampulla cancer or other forms of gastrointestinal cancer, had incomplete medical records, or lost follow-up shortly after diagnosis.
Statistical approach	Statistical methods SPSS 25.0 and Prism 8.0.1 software were used for all statistical analyses.
Expected progress	Expected progress: From April 2024 to May 2024, data collection, sorting and analysis will be completed. From May 2024 to June 2024, monograph writing, submission and conclusion will be completed

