## **2. Study purpose**

2.1 Main Objectives: Whether radical DA resection is associated with improvement in 5-year overall survival

2.2 Secondary objectives: Adjuvant therapy, pancreatic invasion, and advanced tumor stage were identified as significant predictors of overall survival

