## **3. Study endpoint**

3.1 Primary endpoints: Median overall survival, 3 - and 5-year overall survival rates for the cohort

3.2 Secondary endpoints: overall survival with adjuvant therapy, pancreatic invasion, and advanced tumor

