## 5.3 Exclusion criteria:

- (1) Cancer of the ampulla or other forms of gastrointestinal cancer  
Medical records are incomplete
- (2) Diagnostic or therapeutic data is missing
- (3) Follow-up was lost shortly after diagnosis
- (4) The non-ampulla DA patients were judged by the investigators to be unsuitable for participating in this study

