#### 6.4 Data Collection Procedure

- (1) Record demographic data: date of birth, gender, initials;
- (2) Medical history and physical examination (including vital signs, height, weight, BMI, physical examination of all systems; HCC history Present history, etiology)
- (3) Clinical presentation (symptoms, tumor location, stage of diagnosis), treatment modalities (surgical intervention, adjuvant therapy) and survival outcome (survival time, recurrence), details of surgical procedure (resection extent, lymph node dissection);
- (4) Record laboratory test results: including preoperative laboratory values (such as CEA, CA19-9 levels) and available genetic markers Markers (KRAS mutation, dMMR/MSI-H);
- (5) Pathological findings (tumor differentiation, lymphatic vascular infiltration, perineural infiltration) were recorded.

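### The main objective compares survival by radical resection, but the primary endpoint is pooled over the cohort and no adjusted resection analysis is designated or has its covariates fixed

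*Combined protocol and SAP*

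**What the plan says.** Section 2.1 states the main objective: "Whether radical DA resection is associated with improvement in 5-year overall survival". Section 3.1 gives the primary endpoint as "Median overall survival, 3 - and 5-year overall survival rates for the cohort", and the summary table repeats it: "Primary outcome measures for effectiveness analysis: median overall survival, 3 - and 5-year overall survival rates in the cohort". Neither place splits survival by resection status or names a comparison group.

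The survival methods appear only in the summary table. There, "log-rank tests were used to compare the distribution of survival among different patient subgroups", with the subgroups not named. Cox models are to find independent prognostic factors. The variables considered include demographic and clinical features, preoperative laboratory values, and "treatment details (radical resection, adjuvant therapy), and pathological findings (AJCC stage, tumor differentiation and lymph node involvement rate". HRs with 95% confidence intervals "were calculated to estimate the strength of the association between each variable and survival outcomes". Section 10 covers chi-square or Fisher, t and non-parametric tests, the software and the significance level, and names no survival method.

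Section 6.4 records "details of surgical procedure (resection extent, lymph node dissection", and it records stage at diagnosis. Section 5.3 excludes patients where "Diagnostic or therapeutic data is missing". Section 2.2 makes pancreatic invasion a secondary objective. It is named in neither the Cox list nor section 6.4.

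**The concern.** The main objective needs a contrast between two groups, and the primary endpoint is a single-group summary. The contrast could come from the log-rank test or from the Cox model, and the plan does not say which one answers the objective. The cohort takes all stages, so resection status is likely to follow stage closely and a crude comparison would largely reflect stage.

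Within the Cox model two listed variables need a decision. Lymph node involvement rate normally exists only where nodes were removed, so its presence depends on the exposure being studied. Adjuvant therapy comes after surgery: leaving it out gives the association of resection together with what follows it, and entering it gives the association of resection apart from adjuvant therapy. These are different quantities, and the choice between them stays open until results are seen.

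**Working it through.** The only design figure in the plan is 400 patients. It has no derivation, so there is nothing to reproduce. The documents give no stage mix, resection share or survival rates, so **every input below is assumed**.

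**1. A pooled rate does not identify the contrast.** Pooled OS = s × OS(resected) + (1 − s) × OS(unresected), where s is the share resected. Take s = 0.70 and pooled 5-year OS of 40%:
- 0.70 × 40 + 0.30 × 40 = 40: no difference
- 0.70 × 46 + 0.30 × 26 = 40: 20 points
- 0.70 × 52 + 0.30 × 12 = 40: 40 points

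The same primary result fits all three.

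**2. Crude gap from stage alone, with no resection effect.** Base setting: stages I to IV 15/25/35/25%; 5-year OS 75/55/35/5%; radical resection 95/92/85/5%.
- Unresected: 400 × (0.15×0.05 + 0.25×0.08 + 0.35×0.15 + 0.25×0.95) = 400 × 0.3175 = 127.
- 5-year OS, resected: (0.1425×0.75 + 0.23×0.55 + 0.2975×0.35 + 0.0125×0.05) / 0.6825 = 0.3381 / 0.6825 = 49.5%.
- 5-year OS, unresected: (0.0075×0.75 + 0.02×0.55 + 0.0525×0.35 + 0.2375×0.05) / 0.3175 = 0.0469 / 0.3175 = 14.8%.
- Gap 34.8 points; pooled 38.5%.

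The range uses three stage mixes (the base, 20/30/35/15 and 10/20/30/40%), two sets of stage I to III resection shares (95/92/85 and 85/80/65%) and three stage IV shares (5, 20 and 50%), 18 settings in all. The gap runs from 12.6 to 36.8 points, median 24. The base is the second largest.

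**3. Node rate in the resection model, complete cases.** Of the 127 unresected patients in the base setting, 127 × 0.10 ≈ 13 or 127 × 0.25 ≈ 32 remain if 10% or 25% have a node rate. If none has one, the resection HR cannot be estimated. In simulated cohorts of 400 (diagnosis uniform over 2009 to 2023, exponential OS, censoring in spring 2024, 200 cohorts per setting), the 95% CI is the HR times or divided by:

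| Model | Base | Range over settings |
|---|---|---|
| Stage-adjusted, no node rate | about 1.5 | 1.28–1.54 |
| Node rate, 25% of unresected have it | about 2.0 | 1.5–2.1 |
| Node rate, 10% of unresected have it | about 2.5 | 1.8–3.0 |

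**4. Adjuvant therapy in or out.** Base setting, true HR of resection alone 0.60, adjuvant HR 0.7 in half of resected patients (400 cohorts): the resection HR is 0.50 without adjuvant therapy in the model and 0.60 with it. Over adjuvant HRs of 0.6 to 0.8 and 30 to 70% treated, it is 0.42–0.56 without and 0.59–0.61 with. If the adjuvant HR is 1.0 the two agree.

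**5. Pancreatic invasion.** Setting section 2.2 beside the Cox list and section 6.4 shows an objective with no named variable and no named data field.

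**The case against.** The strongest reply is that adjustment is already planned. Radical resection and AJCC stage are in the same Cox list, the stated aim is independent factors, and an HR is promised for each variable. A multivariable model is the natural reading, and nothing offers the crude log-rank test as the answer to the main objective. This stands: it would be wrong to infer that no adjusted analysis is planned. What remains is that the adjusted HR is not tied to the objective and its covariates are only candidates. That the model sits in the summary and not in section 10 is a matter of placement.

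A reader might also infer that node rate would remove most or all of the comparator. The documents do not show this. The cohort comes from a surgical department and section 6.4 records extent of resection, so some patients without radical resection may have had nodes examined; their share is unknown. The exclusion in section 5.3 is an eligibility rule, and applying it to an undefined node rate would sit badly with the all-stage inclusion. Nor does the plan say that missing node rates would be coded as zero, so bias from that coding cannot be charged to it.

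Finally, one might infer that a joint list cannot separate surgery from adjuvant therapy, which section 1 sets as an aim. Step 4 shows the opposite: the model with both recovers the assumed HR for resection alone. Leaving adjuvant therapy out is a choice of a different quantity, not a correction.

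**Conclusion.** The concern holds in this form: the whole-cohort primary endpoint cannot answer the main objective; the implied stage-adjusted resection HR is not designated as its analysis; the plan does not say whether node rate and adjuvant therapy enter that model; and pancreatic invasion has no place in the Cox or data lists. The textual points need no assumption beyond the general one that a node rate normally requires nodes to be removed.

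The sizes are illustrative. The crude gap should be quoted as the 12.6 to 36.8 range with its median of 24; the base value of about 35 points is near the top and should not stand alone. It shows why the log-rank test should not carry the objective, not what the plan will report. The loss of precision from node rate depends on the unknown share of comparator patients who have one. The adjuvant difference vanishes if adjuvant therapy has no effect.

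This should be settled before analysis, because it decides what the study's main result is.

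**What to change.** 1. **Section 3.1:** make 5-year OS by radical resection (yes/no) the primary comparison, say which group non-radical operations fall in, and label whole-cohort median, 3- and 5-year OS as descriptive.
2. **Section 10:** designate one Cox model for the main objective, in all patients: radical resection adjusted for stage at diagnosis (already collected under 6.4), age, sex, BMI, jaundice, bleeding and anemia. Do not enter lymph node involvement rate. Report the adjusted HR with its 95% CI, and treat the log-rank test by resection as descriptive.
3. **Adjuvant therapy:** report the resection HR without it (resection plus what follows) and with it (resection apart from adjuvant therapy, the aim in section 1), label each, and name in advance which is primary.
4. **Secondary objectives:** analyse node rate, adjuvant therapy and pancreatic invasion in a separate model in resected patients. Add pancreatic invasion to the 6.4 data list.
5. **Section 5.3:** state that a node rate undefined because no nodes were removed does not count as missing diagnostic data.

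The cost is protocol text, one chart field and one or two extra models. Confounding by indication, and the interval between diagnosis (when OS starts) and resection, are not removed by this and should be stated as limitations.

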## 1. Study background

Duodenal adenocarcinoma (DA) remains a relatively rare and mysterious entity among gastrointestinal malignancies, accounting for less than 1% of all gastrointestinal cancers, but more than 50% of small bowel cancers. This scarcity has led to poor natural history descriptions of the disease and continued ambiguity around best management strategies. DA is often compared to colorectal cancer because they share a location in the gastrointestinal tract and exhibit similar molecular characteristics and potential pathways for tumor development. However, left and right colon cancers have their unique genomic features and clinical manifestations, which stem from their specific location in the colon. Therefore, tumor location and its genomic profile are considered to be important factors affecting the prognosis of colorectal cancer and small intestinal adenocarcinoma. This underscores the need to treat the outcomes of each DA treatment modality as a distinct entity.

The treatment of DA faces several challenges, including the lack of established guidelines based on worldwide scientific evidence, the difficulty of early detection due to the rarity of the disease and the lack of specific screening markers, and the limited evidence supporting various treatment modalities. Surgical resection is the only possible treatment for DA. The complexity of surgery, which often includes pancreaticoduodenectomy, has evolved over the years, and advances in perioperative care and surgical techniques have helped reduce morbidity and mortality, but there has been no uniform improvement in long-term survival outcomes. Adjuvant therapy, including chemotherapy and radiotherapy, has been explored as a means of improving survival, especially in cases with adverse pathological features, such as lymph node involvement or the advanced stage of diagnosis. Despite these reasons, the efficacy of adjuvant therapy for DA remains controversial. There have been no randomized controlled trials comparing the efficacy of single surgery with perioperative adjuvant treatment for DA. All of the studies were retrospective comparisons of the outcomes of surgery alone and combined surgery, so there may be selection bias in patients. Numerous meta-analyses and systematic reviews have investigated the treatment of DA in depth, but most studies have been retrospective, single-center, and small-sample size series, especially in China. To address this knowledge gap, we conducted a hospital-based cohort study designed to investigate long-

term outcomes in patients with DA and to disaggregate the effects of tumor characteristics, surgery, and adjuvant therapy on survival outcomes.

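### Tumor location is called prognostic and is collected, as are KRAS and dMMR/MSI-H where available, but neither the Cox covariate list nor section 10 names any of them

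*Combined protocol and SAP*

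**What the plan says.** Section 1 (Study background) states that "tumor location and its genomic profile are considered to be important factors affecting the prognosis of colorectal cancer and small intestinal adenocarcinoma". The same section closes by setting out to separate the contributions of tumor features, surgery and adjuvant treatment to survival.

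Section 6.4 collects location in item (3), under "Clinical presentation (symptoms, tumor location, stage of diagnosis". Item (4) covers laboratory results, "including preoperative laboratory values (such as CEA, CA19-9 levels) and available genetic markers Markers (KRAS mutation, dMMR/MSI-H".

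The only covariate list is in the Statistical analysis row of the Summary of research scheme. It begins "Variables considered in the model included demographic factors (age, sex), clinical features (BMI, jaundice, bleeding, anemia), preoperative laboratory values", continues with radical resection and adjuvant therapy, and ends with "pathological findings (AJCC stage, tumor differentiation and lymph node involvement rate". The same row says that "log-rank tests were used to compare the distribution of survival among different patient subgroups", without naming the subgroups.

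Section 10 gives software, descriptive methods, two-group tests and the significance level, but no covariates. The main objective in section 2 is "Whether radical DA resection is associated with improvement in 5-year overall survival". Sections 2 and 3 do not mention location, KRAS or dMMR/MSI-H.

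**The concern.** The protocol gives a reason to care about location and genomic profile, collects both, and then names no analysis that uses them. Two things are at stake.

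First, the stated aim of separating tumor features from treatment is not carried through for these variables. Because their role is left open, they could be added to the model or left out after the results are seen.

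Second, the main objective is a non-randomized comparison. Section 4 leaves treatment to the treating physician, and section 1 itself warns of patient selection in earlier retrospective comparisons. In that setting, a prognostic factor known at diagnosis and already recorded belongs among the candidate adjustment variables. If location also differs between patients with and without radical resection, leaving it out would shift the resection hazard ratio.

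**Working it through.** **Step 1. Compare the sections.** The plan states no figure on this point, so there is nothing to reproduce. The check is one of content.

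| Variable | Section 1 (prognostic) | Section 6.4 (collected) | Cox list (Summary) | Section 10 | Objectives and endpoints (2, 3) |
|---|---|---|---|---|---|
| Tumor location | yes | yes | not named | not named | not named |
| KRAS | as genomic profile | where available | not named | not named | not named |
| dMMR/MSI-H | as genomic profile | where available | not named | not named | not named |

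Three of three are collected, and none of the three has a named analysis. The Cox item on preoperative laboratory values does not clearly cover the markers: section 6.4(4) puts them under the same heading but lists them as a separate item beside those values.

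**Step 2. What omission could do (all inputs assumed).** For an omitted binary factor with hazard ratio H and prevalence p1 in resected and p0 in unresected patients, the resection hazard ratio is multiplied by approximately

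(1 + p1(H − 1)) / (1 + p0(H − 1)).

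The documents give none of H, p1 or p0.

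- p1 = p0 = 0.50: the multiplier is 1.00 for any H.
- p1 = 0.30, p0 = 0.50: H = 1.3 gives 1.09/1.15 = 0.948; H = 1.5 gives 1.15/1.25 = 0.920; H = 2.0 gives 1.30/1.50 = 0.867.
- p1 = 0.50, p0 = 0.30: the ratios invert, so H = 1.3 gives 1.15/1.09 = 1.055 and H = 2.0 gives 1.50/1.30 = 1.154.

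These use crude prevalences. The planned model already includes stage, differentiation and node rate, so what matters is the imbalance left after those terms, which could be smaller.

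**Step 3. Cost in model size (degrees of freedom and deaths assumed).** Count the named list as age 1, sex 1, four clinical features 4, CEA and CA19-9 2, resection and adjuvant therapy 2, stage 3, differentiation 2, node rate 1. The total is 16. Location in two or three groups makes it 17 or 18.

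| Deaths | Per parameter, 16 | 17 | 18 |
|---|---|---|---|
| 160 | 10.0 | 9.4 | 8.9 |
| 200 | 12.5 | 11.8 | 11.1 |
| 240 | 15.0 | 14.1 | 13.3 |
| 280 | 17.5 | 16.5 | 15.6 |

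**Step 4. Why the markers differ from location.** If markers were available in 90%, 70%, 50% or 30% of the 400 patients (assumed), a complete-case main model would keep 360, 280, 200 or 120 of them. Section 6.4 attaches no such availability limit to location.

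**The case against.** A reader might infer that the plan leaves a known confounder unadjusted and that the resection and adjuvant estimates are therefore biased. The documents do not support that reading, and four objections to it have force.

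- **Confounding is not shown.** It needs a link to treatment as well as to outcome. The documents never say that location or the markers relate to receiving radical resection or adjuvant therapy. Location might affect which operation is done without affecting whether radical resection is done, and the latter is the exposure in the main objective. This stands.
- **Section 1 is not about duodenal segment.** It argues from left versus right colon and from the small intestine to treating duodenal tumors as a distinct entity. Restricting the cohort to the duodenum already deals with location in that sense. This stands in part: applying the statement to segment is an inference. But every tumor in the cohort is duodenal, so the location recorded under section 6.4 can vary only within the duodenum.
- **The list may be open.** Its wording can be read as giving examples, and the log-rank subgroups are unnamed. So the variables are unspecified, not excluded. That stands, but it does not close the gap: an open list permits a choice after seeing the data, and an unadjusted log-rank test by location would not adjust the resection estimate.
- **The markers serve no objective or endpoint.** Collecting a variable does not oblige anyone to analyse it, and partial availability is a good reason to keep the markers out of the main model. This stands, and the point does not rest on them.

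**Conclusion.** The point holds as a gap in specification. Location is a recorded baseline factor that the protocol treats as prognostic, and no named analysis uses it, despite the aim of separating tumor features from treatment. It is a potential confounder of the resection estimate, not a demonstrated one.

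Neither the size nor the sign of any bias can be derived from the documents. The multipliers of 0.87 to 0.95 in step 2 depend wholly on the assumed hazard ratios and the assumed 30% versus 50% split. They become 1.00 with no imbalance and exceed 1 if it reverses, so they should not be read as an estimate of bias in this study.

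The case for change rests on low cost and on fixing the choice in advance, not on proof of bias. It carries over only weakly to KRAS and dMMR/MSI-H, for which a clarification is optional.

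**What to change.** In the Statistical analysis row of the Summary of research scheme, add tumor location to the multivariable Cox covariates, defined as duodenal segment in two or three groups fixed before analysis. If the sponsor prefers to leave it out, give the reason in the same place.

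The cost is one line of text and 1 to 2 degrees of freedom. Under the assumptions in step 3, that takes 200 deaths from 12.5 to between 11.1 and 11.8 per parameter. No new data are needed, assuming that the location recorded under section 6.4 identifies the segment.

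Optionally, add a sentence saying that any KRAS or dMMR/MSI-H analysis is exploratory, is confined to tested patients, and stays outside the main model because the markers are recorded only where available. This requires no new tests.

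While that row is open, note that pancreatic invasion, which the secondary objective in section 2 names, is also missing from the Cox list. The same edit can settle it.
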